7. TREATMENT INTERVENTIONS

This study will be a placebo controlled study. Treatment interventions will be described in sections 7.1 - 7.3.

7.1 Randomization to 24 hours

Patients will be randomized as described above to one of 3 treatment combinations:

- Optimal diuretic dosing + placebo
- Optimal diuretic dosing + low dose dopamine
- Optimal diuretic dosing + low dose nesiritide

All patients will be started on a 2 liter per day fluid restriction and a 2 gm per day sodium diet. Decisions regarding the use of standard heart failure medications such as ACE inhibitors, beta blockers and digoxin will be left to the discretion of the treating physicians.

Vascular access

Central venous line or PICC line or standard peripheral IV catheter placed in the antecubital fossa, depending on local hospital requirements, will be placed in the patients randomized to the Dopamine strategy group. Standard peripheral IV catheter will be placed in the patients randomized to the Nesiritide strategy group

Urinary Catheter

Use of an indwelling urinary catheter will be encouraged in all patients but a patient may decline and remain in study.

Study Drug Dose and Supplies

The study site investigational pharmacy will prepare low dose dopamine $(2\mu g/kg/min)$, low dose nesiritide $(0.005 \mu g/kg/min without bolus)$ or placebo (Dextose 5% water). Hospital stock should be used. Clinical personnel, investigators, and the patients will be blinded.

Based on the results from the recently completed DOSE study, the optimal dose of diuretic will be as follows:

IV furosemide (or equivalent) at a dose equivalent to 2.5 x the total daily *outpatient* oral furosemide (or furosemide equivalent) dose twice daily or equivalent dosing over a 24 hour period. The maximum total daily dose to be administered is 600 mg. and the

minimum total daily dose to be administered is 80 mg. (at frequency determined by the local physician). For patients who have not been taking outpatient loop diuretics, they will receive 80 mg/day of IV furosemide (or equivalent) dose. If the outpatient dose has changed over the week prior to admission, the outpatient dose will be defined as that being utilized 7 days prior to randomization. For patients receiving outpatient loop diuretics other than furosemide, conversion to furosemide equivalents will be as follows:

1 mg torsemide = 2 mg furosemide

1 mg bumetanide = 40 mg furosemide

At 24 hrs, the treating physician can chose to change the diuretic dose

- a. Continue current dose without change
- b. Decrease diuretic dose
- c. Increase diuretic dose
- d. Change to oral diuretic

7.2 48 hours

At 48 hrs, the treating physician can chose to change the diuretic dose

- a. Continue current dose without change
- b. Decrease diuretic dose
- c. Increase diuretic dose
- d. Change to oral diuretic

7.3 72 hours and afterwards

After 72 hours, all patient care decisions will be at the discretion of the treating physician.

7.4 Patient Safety, Concomitant Therapies, and Rescue Therapy

Although investigators are encouraged to follow the assigned treatment strategy for the duration of the treatment period (72 hours), in all cases the patient's safety based on the clinical judgment of the treating physician will take priority over the specific treatment assignment.

Patients requiring other intravenous vasoactive medications for heart failure (inotropes, vasodilators, etc) will be excluded. Patients requiring such drugs for clinical reasons during the randomization period will meet the secondary endpoints of "worsening or persistent heart failure" and "treatment failure" (see endpoint section).

In the Nesiritide strategy group, if the subject develops significant hypotension as defined by systolic BP of <85 mmHg or light headedness, dizziness or visual symptoms, the infusion will be stopped. After 3 hours, if systolic BP is > 90 mmHg and there is resolution of symptoms, the IV infusion will be restarted at 0.0025 μ g/kg/min (50% of the previous dose). If the systolic blood pressure after 3 hours is <90 mmHg or hypotension recurs, then the infusion will be terminated and this will be captured as "treatment failure"

In the Dopamine strategy group, if the subject develops tachycardia as defined by heart rate of >120 beats per min the infusion will be stopped. After 3 hours, if heart rate is < 120 beats per min, the IV infusion will be restarted at 1 μ g/kg/min (50% of the previous dose). If the heart rate is >120 beats per min after 3 hours or if tachycardia recurs, then the infusion will be terminated and this will be captured as "treatment failure"

As this is a randomized trial comparing initial strategies, in either case the interpretation of the primary endpoints with regard to both efficacy and renal function will be on an "intention to treat" basis.

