5. BASIC STUDY DESIGN

This study is a randomized, double blind, placebo controlled, multi-center clinical trial of patients with signs and symptoms consistent with AHF within 24 hours of hospital admission. A total of approximately 360 patients will be enrolled in the trial.

Patients will be randomized to one of 3 treatment regimens (120 patients / treatment regime):

- 1. Optimal diuretic dosing + placebo
- 2. Optimal diuretic dosing + low dose dopamine
- 3. Optimal diuretic dosing + low dose nesiritide

Central venous line or PICC line or standard peripheral IV catheter placed in the antecubital fossa, depending on local hospital requirements, will be placed in the patients randomized to the Dopamine strategy group. Standard peripheral IV catheter will be placed in the patients randomized to the Nesiritide strategy group

ROSE protocol Amendment 1: March 24, 2011

TThere will be an initial open 1:1 randomization to a Nesiritide Strategy group or a Dopamine Strategy group. Patients in the Dopamine Strategy group will subsequently be randomized to low dose dopamine or placebo in a 2 to 1 blinded fashion. Likewise patients in the Nesiritide Strategy group will be randomized to low dose nesiritide or placebo in a 2 to 1 blinded fashion. All patients will receive open-label diuretic treatment.

Figure 4

For testing the primary hypotheses outlined in Section 2.1, the placebo patients will be pooled, so that patients randomized to receive dopamine will be compared with the pooled placebo group, and similarly, patients randomized to receive nesiritide will be compared to the pooled placebo group.

The study treatment regimen will be administered for *a total duration of* 72 hours, unless clinical reasons require discontinuation earlier.

The investigator may modify the diuretic dose at 24 and / or 48 hours. The primary assessment for both efficacy and safety will occur at 72 hours after randomization. **After** the primary assessment at 72 hours, all treatment will be open label at the treating physician's discretion.

The primary safety endpoint will be change in serum cystatin C from randomization to 72 hours, based on a standardized, blinded core lab assessment. The primary endpoint for efficacy will be cumulative urinary volume (UV; indwelling urinary catheter) at 72 hours.

Patients will be followed daily during hospitalization for assessment of serious adverse events.

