11.2 Secondary Endpoints

- Change in serum creatinine from randomization to 72 hr
- Cumulative urinary sodium excretion (UNaV) at 72 hr
- Patient global well being assessment by VAS AUC over 72 hr
- Dyspnea assessment by VAS AUC over 72 hr
- Change in weight from randomization to 72 hr
- Change from randomization in blood urea nitrogen (BUN) / serum cystatin C ratio

at 72 hr

• Development of Cardio-renal syndrome: defined as increase in serum creatinine

> 0.3 mg/dl from randomization at any time point during 72 hours after

randomization

- Persistent or worsening heart failure defined as need for rescue therapy (additional IV vasoactive agent for heart failure treatment, ultrafiltration, mechanical circulatory or respiratory support) over 72 hours after randomization.
- Treatment Failure, a composite comprised of ANY ONE of the following during the 72 hours after randomization:
 - o development of cardio-renal syndrome as defined above
 - o worsening/persistent heart failure as defined above
 - Significant hypotension requiring discontinuation of study drug
 - Significant tachycardia requiring discontinuation of study drug
 - o death

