13.4 Analysis of Secondary and Tertiary Endpoints

General linear models and nonparametric approaches will be used to analyze the continuous outcomes. For binary outcomes, logistic regression analysis will be used to compare each treatment vs. placebo and estimate the odds ratio and 95% confidence interval for low-dose dopamine vs. placebo and low-dose nesiritide vs. placebo comparisons. Time-to-event comparisons will be conducted using Kaplan-Meier curves and log-rank tests. For analyses of patient global well being VAS and dyspnea VAS, the value of zero will be imputed for all measurements missing due to death. Sensitivity analyses, including the worst-rank score analysis ⁽²¹⁾ will be employed to assess the influence of informatively missing values on the results. In particular the worst-rank score analysis will account for missing data due to deaths.

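### Treatment failure counts hypotension stops ruled only in the nesiritide strategy and tachycardia stops ruled only in the dopamine strategy, and Section 13.4 does not tie each drug to placebo from its own strategy

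*Protocol*

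**What the plan says.** Section 7.4 ties each rule to one strategy: "In the Nesiritide strategy group, if the subject develops significant hypotension as defined by systolic BP of <85 mmHg" (or has listed symptoms) the infusion stops, and "In the Dopamine strategy group, if the subject develops tachycardia as defined by heart rate of >120 beats per min" it stops. After a failed three-hour check or a recurrence, each paragraph continues "then the infusion will be terminated and this will be captured as" treatment failure. Neither paragraph has a counterpart for the other strategy.

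Section 11.2 defines the treatment-failure composite with no restriction by strategy. Two of its five components are "Significant hypotension requiring discontinuation of study drug" and "Significant tachycardia requiring discontinuation of study drug".

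Section 5 describes an "initial open 1:1 randomization to a Nesiritide Strategy group or a Dopamine Strategy group", followed by blinded 2:1 allocation to drug or placebo within each strategy. Staff therefore know which rule applies to a patient, including a placebo patient.

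Sections 5 and 13.2 pool placebo across strategies for the primary comparisons, and Section 13.2 puts a strategy indicator in that model. For binary secondary endpoints, Section 13.4 says that "logistic regression analysis will be used to compare each treatment vs. placebo". It mentions neither a strategy indicator nor a same-strategy control.

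**The concern.** With 360 patients, 1:1 by strategy and 2:1 within it, the hypotension rule covers 120 nesiritide and 60 placebo patients. The tachycardia rule covers 120 dopamine and the other 60 placebo patients. If the 120 placebo patients are pooled, every patient in an active arm is under one rule while half of the controls are under another. Part of any difference in treatment failure would then reflect which rule applied, not what the drug did.

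The co-primary endpoints, 72-hour cystatin C change and urine volume, do not count these stops. Yet the strategy indicator is specified for them and not for the endpoint whose capture depends on strategy. At stake is the reading of treatment failure, and of any tabulation of its hypotension and tachycardia stops, for each drug.

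**Working it through.** **Plan's own figure.** The protocol gives no rate, power or sample size for treatment failure. Its power figures concern the co-primary endpoints and reproduce (cystatin C: 102 per group, difference 0.3 mg/L, SD 0.62 mg/L, two-sided 0.025 gives 88.4% by t-test, stated 88%). They do not bear on this point.

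**Inputs.**
- Group sizes: 120 + 60 in each strategy (Sections 5 and 9.1).
- b, failure from the other components: 25%, an assumption. Section 3 cites worsening renal function in 25-30% of such admissions.
- h, untreated stop rate under the hypotension rule: 6%, an assumption. It is the second-listed rate of discontinuation for hypotension (13% vs. 6%) in the 48-hour nesiritide trial in patients with renal dysfunction, Section 4.2.
- t, untreated stop rate under the tachycardia rule: not in the protocol, so varied.
- Components independent; the drug does nothing; at first, no stops outside the rules.

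**Formula.** Expected failure is pN = 1-(1-b)(1-h) for every nesiritide-strategy patient and pD = 1-(1-b)(1-t) for every dopamine-strategy patient. Pooled placebo is (pN+pD)/2. The null difference is therefore pN-(pN+pD)/2 = (1-b)(h-t)/2 for nesiritide, and its negative for dopamine. It is zero only if h = t.

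**Worked case, t = 0.** pN = 1-0.75×0.94 = 0.295; pD = 0.25; pooled = 0.2725. Null difference 0.75×0.06/2 = 2.25 points. Nesiritide OR = (0.295/0.705)/(0.2725/0.7275) = 1.12; dopamine OR = (0.25/0.75)/(0.2725/0.7275) = 0.89.

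**Range at b = 25%.** Type I error is for a two-sided 0.05 two-proportion test, 120 vs 60+60, by exact enumeration.

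| h | t | Null difference, nesiritide (points) | Null OR, nesiritide / dopamine | Type I error, nesiritide / dopamine |
|---|---|---|---|---|
| 6% | 0% | +2.3 | 1.12 / 0.89 | 6.7% / 6.8% |
| 6% | 3% | +1.1 | 1.06 / 0.95 | 5.4% / 5.4% |
| 6% | 6% | 0 | 1.00 / 1.00 | 5.0% / 5.0% |
| 6% | 10% | -1.5 | 0.93 / 1.07 | 5.7% / 5.6% |
| 20% | 0% | +7.5 | 1.39 / 0.69 | 22.9% / 24.9% |

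The second row also describes off-rule stops. If hypotension stops reach 6% in the nesiritide strategy and 3% in the dopamine strategy, with no tachycardia stops, the arithmetic is the same.

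**Effect of the strategy term.** There are four cells: each drug and its own placebo. An intercept, two drug indicators and a strategy indicator fit them exactly, so each drug's OR becomes its same-strategy OR. In a large simulated data set (b = 25%, h = 6%, t = 0), the null ORs were 1.12 and 0.89 without the indicator and 1.007 and 0.998 with it.

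**Precision.** (1/120+1/60)/(1/120+1/120) = 1.5.

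**The case against.** The strongest reply is that the criticised analysis is inferred. Pooling is stated only for the primary hypotheses, Section 13.4 names no covariates, and a statistical analysis plan, not available here, may settle both. This stands as far as the wording goes: Section 13.4 does not say that placebo is pooled for treatment failure or that strategy is left out. What remains is that the unequal stop rules are fixed in Section 7.4 itself, and that Section 5 defines a single placebo regimen, so a reader of Section 13.4 will naturally pool.

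Second, Section 11.2 is not restricted by strategy, and Section 7.4 says that "in all cases the patient's safety based on the clinical judgment of the treating physician will take priority". A dopamine-strategy patient stopped for hypotension can meet the composite. This also stands. Such stops shrink the distortion, but they follow no rule and are made by staff who know the strategy.

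Third, 6% is only a proxy. It comes from another trial, and Section 7.4 counts failure only at final termination. That stands, which is why the figures are illustrations.

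Fourth, pooling can be the more accurate choice when the distortion is small. In the worked case the bias in the nesiritide log OR is 0.11 against a standard error of about 0.29, a root mean squared error of about 0.31; the same-strategy standard error is about 0.35. At an assumed h = 13%, t = 0, the order reverses: 0.36 pooled (bias 0.22, standard error 0.28) against 0.33. Since h and t are unknown, a comparison free of this bias is the safer one to specify.

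Two stronger readings are tempting. A reader might infer that the comparison is biased whatever happens; the equal-rates case gives no bias. A reader might also take the hypotension stops alone, where 6% against 3% gives a null OR of (0.06/0.94)/(0.03/0.97) = 2.06, as the size of the problem. Section 11.2 makes only the composite an endpoint and plans no separate test of that component.

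The comparison of the two placebo groups in Section 13.5 is exploratory, aimed at the PICC line, and corrects nothing.

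**Conclusion.** The point holds conditionally. Under the natural reading of Section 13.4, treatment failure is ascertained by a different rule in half of each drug's controls. A null drug then departs from placebo unless the two rules stop untreated patients equally often, and nothing in the protocol supports that equality. The departures have equal size and opposite sign for the two drugs on the risk-difference scale.

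At 25% background failure and 6% hypotension stops, the composite is off by about 2 points at most for t between 0 and 10%, with type I error below 7%. It becomes serious only with much higher stop rates or a lower background. The direction cannot be determined, because no tachycardia stop rate is given. The documents do not support a claim of demonstrated bias of known size. They do support correcting an avoidable weakness in one of nine secondary endpoints; the primary conclusions are untouched.

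**What to change.** In Section 13.4, state that treatment failure, and any report of its hypotension and tachycardia stops, is compared with same-strategy placebo (120 vs 60) or, equivalently, that the logistic model carries the strategy indicator of Section 13.2. The composite without these two components may be shown against pooled placebo as a supporting analysis.

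Reconcile Sections 7.4 and 11.2 on how each kind of stop is captured in each strategy, including stops made on clinical judgment. No change to the stopping rules is proposed.

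The cost is a sentence or two of text and a wider interval for this secondary endpoint: the variance of the difference is about 1.5 times larger, so the interval is about √1.5 = 1.22 times as wide.

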8. RECRUITMENT AND SCREENING PROCEDURES

8.1 Common Recruitment/Screening Procedures

All patients admitted to the participating Heart Failure Clinical Research Network centers with signs and symptoms suggestive of AHF will be screened by a study coordinator. Given the short time period after admission (≤ 24 hours) for inclusion in the study, it is anticipated that screening in the Emergency Department and screening more than once daily will be effective recruitment strategies. Patients meeting eligibility criteria will be approached regarding participation in this study.

8.2 Estimated Enrollment Period

This study will enroll 360 patients at 9 Regional Clinical Centers (RCCs) and associated satellite centers in the United States and Canada. It is projected that 18 patients per month will be enrolled (2 pts/RCC/month), for a total anticipated enrollment period of approximately 20 months.

8.3 Informed Consent Procedures

8.3.1 Informed Consent

All patients will have the purpose of the study, the study interventions and evaluations, and the potential risks and benefits of participation explained to them and their questions answered. If they consent to participation in this study, they will review and sign the informed consent form (ICF). A template for the ICF appears in Appendix D.

8.3.2 Confidentiality and HIPAA Requirements

All information collected on study participants will be stored in a confidential manner using procedures in place at each participating RCC and associated satellite centers. Only approved study personnel will have access to data collected as part of the ROSE Study. Study participants will be identified by a Subject ID # on all study documents. Data will be

transmitted to the DCC in a secure manner, and stored securely at the DCC using standard DCRI operating procedures.

8.3.3 Protections of Human Subjects

All research proposed in this application will be performed in accordance with applicable human subjects protection regulations.

A copy of the protocol, proposed informed consent form, other written information and any proposed advertising material must be presented to each site's Institutional Review Board (IRB) for written approval prior to enrollment of subjects. A copy of the written approval of the protocol and informed consent must be retained by the site in a study file. The investigator must submit and obtain approval from the IRB for subsequent protocol amendments and changes to the consent before implementing such changes. The investigator will notify the IRB of deviations from the protocol or serious adverse events occurring at the site. Each site must have IRB approval prior to enrolling any patients in the study.

8.3.4 Summary of the Risks and Benefits

As renal function is an important prognostic factor in patients with AHF, the patients randomized to the treatment groups may potentially benefit from the study. The risks of the study are:

- Low dose dopamine: **Common**: Chest pain, increase in blood pressure, fast or irregular heart rates, injection site reaction and hair follicles could stand erected
- Low dose nesiritide: **Common:** Low blood pressure nausea, dizziness; headache; insomnia; worsening of renal function at doses that are higher than what is used in this study. **Uncommon:** irregular heart rhythm, allergic reaction and increased risk of death
- The risks of blood drawing include bleeding at the puncture site, bruising and pain. These risks occur in a very small portion of the population. Patients with a hemoglobin < 9 g/dl will be excluded.
- The risk for PICC line placement include bruising, fainting, pain, swelling, scarring, bleeding, infection, a decrease in blood pressure, slowing of heartbeats, sweating and a feeling of weakness or lightheadedness. Uncommon risk includes infection at the site of the needle stick. These reactions generally do not cause any permanent harm. If a central line is needed, there may be additional risk of pneumothorax.
- This protocol may be hazardous to an unborn child. There is no medical information to determine whether there are significant risks to a fetus carried by a mother who is participating in this study. Therefore, female participants must be postmenopausal or have been surgically sterilized or have a serum negative pregnancy test.

9. BASELINE EVALUATIONS AND RANDOMIZATION

A complete schedule of assessments throughout the study is given in Appendix A.

9.1 Randomization

After providing informed consent and signing the ICF, all study subjects will be randomized using procedures determined by the DCC to one of 3 treatment groups. **Patients will be randomized to the nesiritide or dopamine strategy in a 1:1 allocation ratio.** Within each strategy, subjects will be randomized to active drug vs. placebo in a 2:1 allocation ratio. A permuted block randomization method stratified by site will be used to ensure relatively equal distribution of subjects to each arm within each clinical site.

9.2 Baseline Assessments

At the time of randomization, all study subjects will undergo

- Directed history and physical examination, focused on signs and symptoms of congestion
- Vital signs (including O₂ saturation and weight)
- Concomitant cardiovascular medications
- Serum Cystatin C (core laboratory)
- Serum creatinine, BUN, and electrolytes (local laboratory)
- Patient Global Well being assessment (PGA) by VAS (see Appendix C)
- Dyspnea assessment by VAS (see Appendix C)
- Blood sample for biomarkers core laboratory
- Urine Biomarkers

10. FOLLOW UP EVALUATIONS

The 24-hour assessment should occur between 22 and 26 hours after randomization. The 48-hour assessment should occur between 46 and 50 hours after randomization. The 72-hour assessment should occur between 70 and 74 hours after randomization.

The protocol described assessments and urine collection times should be based on the randomization date and time as the anchor. Urine should be collected from randomization through 72 hours. In instances where the start of study drug is delayed 6 or more hours after randomization, an additional urine collection for assessing urinary sodium excretion is required. This urine collection would begin at the 72 hour from randomization point and end at the conclusion of the 72 hour study drug infusion point.

10.1 24, 48 and 72 hours

Between randomization and 72 hours, all study subjects will undergo the following assessments daily:

- Directed history and physical examination, focused on signs and symptoms of congestion
- Vital signs (including O₂ saturation and weight)

- Serum Cystatin C (core laboratory)
- Serum creatinine, BUN, and electrolytes (local laboratory)
- PGA assessment by VAS at 24, 48, and 72 hours
- Dyspnea assessment by VAS at 24, 48 and 72 hours
- Fluid balance between randomization and 24 hours (net intake net output), 24 and 48 hours, and 48 and 72 hours
- Blood sample for biomarkers core laboratory
- Changes in cardiovascular medications
- Assessment for serious adverse events
- Urine biomarkers
- Urine collection for UNaV

